11.3 Potential benefits of clinical monitoring and virologic testing

Subjects enrolled in the study may reduce their chances of disease progression.

11.4 Potential risks

1. Risks of plasma: Fever, chills, rash, headache, serious allergic reactions, TRALI, TACO, transmission of infectious agents
2. Risks of phlebotomy: local discomfort, bruising, hematoma, bleeding, fainting,
3. Total blood draws will not exceed 500 mL
4. Risks of oropharyngeal and throat swab: local discomfort, vomiting

11.5 Alternatives

The alternative to participation in this study is routine care.

12.0 ADVERSE EVENTS AND SAFETY EVALUATION

Adverse events will be evaluated and scored using Common Terminology Criteria for Adverse Events version 5.0 (CTCAE v5.0). ctep.cancer.gov/.../CTCAE_v5_Quick_Reference_5x7.pdf

1. Safety Evaluations will assess for the safety of high titer anti-SARS-CoV-2 plasma
2. Clinical evaluations: Vital signs and symptom screen on days 0-7, 14 and symptom screens on days 28, and 60.
3. Safety Evaluations will assess for the safety of high titer anti-SARS-CoV-2 plasma
4. Clinical evaluations: Vital signs and symptom screen on days 0-7, 14 and symptom screens on days 28, and 60.
5. Laboratory evaluations consistent with ongoing medical care may include radiographic imaging modalities such as chest x-rays and chest CT.
6. Safety laboratory tests (ABO typing, pregnancy testing, CBC, CRP, and comprehensive metabolic panel) will be performed at the local CLIA-certified clinical laboratory on days 0-7 and 14.

12.1 Adverse Event (AE)

Any untoward medical occurrence in a clinical investigation subject who has received a study intervention and that does not necessarily have to have a causal relationship with the study product. An AE can, therefore, be any unfavorable and unintended sign (including an abnormal laboratory finding, for example), symptom, or disease temporally associated with the use of the study product, whether or not considered related to the study product.

12.2 Serious Adverse Event (SAE)

An SAE is any adverse event that results in any of the following outcomes:

1. Death
2. Life-threatening (immediate risk of death)
3. Prolongation of existing hospitalization

4. Persistent or significant disability or incapacity
5. Important medical events that may not result in death, be life threatening, or require intervention or escalation of care may be considered a serious adverse event when, based upon appropriate medical judgment, they may jeopardize the subject and may require medical or surgical intervention to prevent one of the outcomes listed in this definition. Examples of such medical events include allergic bronchospasm requiring intensive treatment in an emergency room or at home, blood dyscrasias or convulsions that do not result in inpatient hospitalization.

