9. Blood for Immune evaluations of cellular and humoral immunity (4 green tops, 30-40 milliliters).

Day 1-7 (or for duration of hospitalization)

1. Vital signs daily (including supplemental oxygen requirements)
2. COVID-19 symptom screen (fevers, cough, shortness of breath)
3. Assessment of clinical status (8-point ordinal scale)
4. New medical conditions, AE evaluation
5. Physical examination
6. CBC with differential, comprehensive metabolic panel, CRP daily

Days 0, 4 (\pm 1 day), 7 (\pm 2 day), 14 (\pm 3 days), 21 (\pm 3 days), and 28 (\pm 3 days):

1. SARS-CoV-2 PCR from oropharyngeal or nasopharyngeal swabs: Day 0, 4, 7, 14, 21 and at any time when there is clinical suspicion for COVID-19.
2. Serum or plasma antibody titer to SARS-CoV-2: Day 0, 7, 14, and 28
3. Blood for immune evaluations of cellular and humoral immunity before CIP infusion (day 0) and 7, 14, and 28 days after CIP infusion (4 green tops, 30-40 milliliters). Immune testing may be done at any time if the PI determines there is a need to evaluate acute immune responses (cytokines/chemokines levels).

Key issues to consider follow up by phone, alive, at home, in hospital (ICU or not), on supplemental O₂ or not, back to work, fully and partially

- COVID-19 symptom screen (fevers, cough, shortness of breath)
- Assessment of clinical status (8-point ordinal scale)
- New medical conditions, AE evaluation

Day 60 (\pm 7 days):

1. COVID-19 symptom screen (fevers, cough, shortness of breath)

2. Assessment of clinical status (8-point ordinal scale)
3. New medical conditions, AE evaluation

One year (\pm 1 month) - *optional*

- 1. Serum or plasma antibody titer to SARS-CoV-2**
- 2. Blood for immune evaluations of cellular and humoral immunity**
- 3. CBC with differential, Comprehensive metabolic panel, PT/INR, PTT, Quantitative immunoglobulins**
- 4. Interval medical history**
- 5. Subject questionnaires regarding health status**

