9.3 Analysis of AE data

Analysis of AE data will primarily be descriptive based on MedDRA coding of events. The proportion of subjects experiencing an SAE and the proportion experiencing a Grade 3 or higher will be recorded. AE will be compared to published data.

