12.10 Assessment of Seriousness

1. Event seriousness will be determined according to the protocol definition of an SAE

2. Assessment of Severity

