14.0 SAFETY OVERSIGHT

14.1 Monitoring Plan

1. All AE and SAW will be reviewed by protocol team in real time.
2. A medical monitor will be appointed by the sponsor for safety oversight of the clinical study.
3. A data safety monitoring board (DSMB) composed of independent experts without conflict of interests. The Board will review the study before initiation and every 3 months thereafter. The Board will review study data to evaluate the safety, efficacy, study progress, and conduct of the study
4. An Independent Safety Monitor (ISM) will be appointed. The ISM is a physician with expertise in infectious diseases and whose primary responsibility is to provide timely independent safety monitoring. An ISM is in close proximity to the study site and has the authority to readily access study participant records. The ISM reviews any SAE that occurs at the study site in real time and provides a written assessment.

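### The SAE definition in section 12.2 omits new inpatient hospitalization, so a readmission after discharge counts as serious only if an investigator chooses to apply the discretionary item 5

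*Combined protocol and SAP*

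**What the plan says.** Section 12.2 opens with "An SAE is any adverse event that results in any of the following outcomes" and gives five items: death; immediate risk of death; "Prolongation of existing hospitalization"; lasting or significant disability or incapacity; and important medical events. The fifth is a matter of judgment: such events "may be considered a serious adverse event when, based upon appropriate medical judgment, they may jeopardize the subject". Its examples include "blood dyscrasias or convulsions that do not result in inpatient hospitalization". Section 12.10 adds: "Event seriousness will be determined according to the protocol definition of an SAE".

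Follow-up continues after discharge. Section 5.2.7 runs it to day 60 and, for the contacts up to day 28, prompts staff to consider "follow up by phone, alive, at home, in hospital (ICU or not". Section 5.2.7 and Table 1 both schedule AE evaluation through day 60.

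Two provisions depend on the SAE label. In section 14.1, "The ISM reviews any SAE that occurs at the study site in real time and provides a written assessment". In section 9.3, "The proportion of subjects experiencing an SAE and the proportion experiencing a Grade 3 or higher will be recorded".

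Section 12.8 limits the recording of AEs and SAEs to 7 days from the first infusion, or until the subject leaves the study if that is sooner. For the time after that it mentions only SAEs suspected to be related to the product, in a sentence that breaks off before stating an action.

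**The concern.** All recipients are inpatients when infused, which may explain why only a longer stay was listed. But they enter from a non-ICU bed on at most 6 L/min of oxygen, and a Table 1 footnote allows for discharge before day 7. Some will be at home for much of the 60 days, and harm that appears after discharge may show itself as a return to hospital. The plan collects that fact but does not automatically class it as serious.

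Two things are at stake: whether the Independent Safety Monitor gives a prompt written assessment of the event, and whether the subject enters the SAE proportion. With 29 treated subjects, one misclassified subject visibly moves that proportion.

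**Working it through.** No figure in the plan can be reproduced here, because the point concerns the wording of a definition. The check sets the sections side by side, with one piece of arithmetic for scale.

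1. **Is the criterion absent?** The items in 12.2 are numbered 1 to 5 without a break, so none appears to have been lost from the text. None names a new hospital admission, and no other section adds it.

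2. **Does the document itself expect it?** The item 5 examples are events that stop short of inpatient hospitalization. That qualifier makes sense only if hospitalization is already a listed outcome. As written, a convulsion managed without admission is a named example of a possible SAE, while the same convulsion leading to readmission matches none of items 1 to 4 unless it is also life-threatening or disabling.

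3. **Does item 5 close the gap?** Only by discretion. It also refers to intervention that prevents one of the listed outcomes. Since hospitalization is not listed, an intervention that averts an admission does not qualify on that ground.

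4. **When does the gap act on its own?** Reading 12.2 with 12.8:
   - *Readmission within 7 days of first infusion:* inside the recording window, so 12.2 decides whether it is an SAE.
   - *Readmission after day 7, suspected to be related to plasma:* 12.8 refers to it only if it is already an SAE, so 12.2 again decides. The action to be taken is not stated.
   - *Readmission after day 7, not suspected to be related:* outside the 12.8 window whatever 12.2 says. Amending 12.2 alone would not secure its recording as an SAE.

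5. **Size.** The denominator is the 29 subjects to be treated (2.3). Section 9.3 counts subjects, not events, so only a subject with no other SAE changes the result:
   - effect per affected subject = 1/29 = 0.034, or 3.4 percentage points.
   - The number of affected subjects cannot be derived, because the documents give no readmission rate.

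**The case against.** The strongest case on the other side has four parts.

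- **Other reviewers still see the event.** The protocol team reviews all AEs in real time (14.1), the Data and Safety Monitoring Committee reviews all AEs (16.2), and the Safety Review Committee reviews cumulative AEs (16.3). On the 12.10.1 scale a readmission would plausibly be grade 3, so it could enter the grade 3 or higher proportion in 9.3. This stands: what is lost is the SAE label, the monitor's written assessment and the SAE count, not all oversight. A reader might infer that readmissions go unreviewed; the documents do not support that.

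- **Section 12.8 is the larger cause of late losses.** This also stands. A reader might attribute every uncounted readmission up to day 60 to 12.2, but for unrelated events after day 7 the recording window is sufficient by itself.

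- **Item 5 may be applied.** Qualified clinicians decide seriousness (12.9), and many readmissions could reasonably be judged to jeopardize the subject. This limits the frequency of the problem but leaves classification to individual judgment.

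- **The consequences can be overstated.** Expedited reporting under 13.0 is for reactions that are both serious and unexpected, so the SAE label alone would not trigger it. The SAE endpoint in 7.3.2 is one of several secondary endpoints and names transfusion-related events, so the clearer effect is on 9.3. Section 9.3 also compares AEs with published data, but the documents do not say whether those sources count readmission as serious, so no distortion of that comparison can be shown.

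**Conclusion.** The gap in 12.2 is real and can be verified from the text. A readmission after discharge that is not fatal, life-threatening or disabling is an SAE only by discretion, and it can miss the monitor's SAE review and the SAE proportion. The supportable size is 3.4 percentage points per subject whose only serious event is an unclassified readmission.

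A larger total is tempting. If 5% to 15% of recipients were readmitted by day 60, that would be 0.05 × 29 = 1.45 to 0.15 × 29 = 4.35 subjects. Rounded to 1 to 4 subjects, this is 3.4 to 13.8 percentage points. The documents do not support that as an estimate. The rate is a pure assumption, and the result also needs every readmission to day 60 to fall within the recording window, none to meet another criterion, item 5 never to be used, and no readmitted subject to have another SAE.

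The correction is worth making because the definition contradicts its own examples and the change is cheap. It achieves its purpose through day 60 only if 12.8 is dealt with at the same time.

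**What to change.** Make two changes in one amendment.

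- **Section 12.2, item 3:** reword it to cover inpatient hospitalization, stating that readmission after discharge is included, as well as the prolongation already listed.
- **Section 12.8:** reconcile the 7-day recording window with the AE evaluation scheduled through day 60 in 5.2.7 and Table 1, and complete the unfinished sentence on later SAEs suspected to be related to the product.

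The cost is a short amendment, a slightly higher reported SAE count and a few more reviews by the Independent Safety Monitor.

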12.3 Unexpected Adverse event: (UAE)

An adverse reaction, the nature or severity of which is not consistent with the investigator's brochure.

12.4 Serious and Unexpected Suspected Adverse Reaction (SUSAR)

12.5 Unanticipated Problem (UP)

Unanticipated Problem that is not an Adverse Event (e.g. breaches of confidentiality, accidental destruction of study records, or unaccounted-for study drug).

Protocol Deviation: Deviation from the IRB-approved study procedures. Designated serious and non-serious

1. Serious Protocol Deviation: Protocol deviation that is also an SAE and/or compromises the safety, welfare or rights of subjects or others
2. Safety Reporting Requirements

12.6 Unanticipated Problem that is not an Adverse Event

(e.g. breaches of confidentiality, accidental destruction of study records, or unaccounted-for study drug.)

12.7 Protocol Deviation

Deviation from the IRB-approved study procedures. Designated serious and non-serious

1. Serious Protocol Deviation: Protocol deviation that is also an SAE and/or compromises the safety, welfare or rights of subjects or others
2. Safety Reporting Requirements

12.8 Reporting Interval

All AEs and SAEs will be documented from the first administration of study product and for the following 7 days or until un-enrollment from the study, whichever comes sooner. All AEs and SAEs will be followed until resolution even if this extends beyond the study-reporting period. Resolution of an adverse event is defined as the return to pre-treatment status or stabilization of the condition with the expectation that it will remain chronic.

At any time after this 7 day period, if the investigator becomes aware of a SAE that is suspected to be related to study product

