2. Age \geq 18 years of age
3. No receipt of convalescent plasma

Immunologic Controls:

1. PBMCs with 5-10 million cryopreserved cells per specimen present in the prospective COVID 19 Biorepository
2. Serum or plasma 500 UI each from up to 50 patients present in the COVID-19 Biorepository

Assessment and Data Acquisition:

1. Baseline: Age, sex, comorbidities, date of symptom onset, known COVID-19 contact, type of admission to the floor or ICU, APACHE score (ICU scoring system to classify disease severity and mortality risk), SOFA score (mortality prediction score based on organ function), clinical status, vital signs including temperature, respiratory rate, oxygen saturation, oxygen requirement, neutrophil count, lymphocyte count, CRP, chest x-ray, chest CT, location in hospital.
2. Safety and efficacy: Day 0 (baseline), 1, 2, 3, 4, 7, 14, 21, and 28 and once at day 60.
3. SARS-CoV-2 PCR from OP or NP swabs: Day 0, 4, 7, 14 and at any time when there is clinical suspicion for COVID-19.
4. Outcome measures: increased O₂ requirement (PaO₂/FiO₂ ratio or SpO₂/FIo₂), supplemental oxygen strategy (nasal cannula, high flow nasal cannula, noninvasive ventilation, intubation and invasive mechanical ventilation, rescue ventilation i.e. neuromuscular blocking agents, prone positioning, corticosteroids, ECMO), vasopressors, renal support, ICU LOS, ICU mortality, hospital LOS, hospital mortality, 28 day mortality.
5. Serum or plasma antibody titer² to SARS-CoV-2: Day 0, 7, 14, and 28. Samples from the COVID-19 Biorepository from non-transfused patients will be assayed at two similar timepoints as Immunologic Controls.
6. Blood for immune evaluations of cellular and humoral immunity before CIP infusion (day 0) and 7, 14 and 28 days after CIP infusion. Immune testing may be done at any time if the PI determines there is a need to evaluate acute immune responses (cytokines/chemokines levels). Samples from the Prospective COVID-19 Biorepository from non-transfused patients will be assayed at two similar timepoints as Immunologic Controls.
7. "Clinical controls" will have all relevant datapoints collected via chart review (i.e. biospecimens will not be collected prospectively)

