6.0 PREPARATION OF CONVALESCENT IMMUNE PLASMA

The plasma product will be collected from **directed**-donors or anonymous donors from the American Red Cross, New York Blood Center, or other local blood donation facility 28 days after symptom resolution. Antibody titers may be assessed by prescreening 21 days after symptom resolution with an anti-SARS-COV-2 titer of preferably >1:64 and/or by measuring titers from the infused plasma. We will use an FDA-approved test to measure antibodies, such as the Ortho Clinical Diagnostic or equivalent test for total IgG, IgM, and IgA directed at COVID-19 spike protein. Donors may be recruited from COIV-19 Screening Clinics, Employee Health Clinics within the health system and by social media advertising. Per current FDA recommendations and ARC practices, it is assumed that by day 28 after symptom resolution, that there will be no viable viral COVID-19 in the circulation. Otherwise the donor will fulfill all of the standard donor criteria for plasma donation.

Donors and samples will have been screened for transfusion-transmitted infections (e.g. HIV, HBV, HCV, WNV, HTLV-I/II, T.cruzi, ZIKV) both through the use of the uniform donor questionnaire and FDA mandated blood donor screening tests. Plasma will have been collected by the ARC or local donation site using standard apheresis technology and in accordance with standard FDA and blood bank protocols. The CIP will be in standard plasma unit bags with storage, handling, and release per blood bank guidelines. The patient will receive 1-2 units of anti-SARS-CoV-2 convalescent plasma.

Table Treatment Schedule	I: Screen n	Baseline	Transfusion	Follow-up							
				1	4±1	7±2	14±3	21±3	28±3	60±7	1 year
Day	-1 to	0	0	1	4±1	7±2	14±3	21±3	28±3	60±7	1 year

	0				day	day	days	days	days	days	±1 month ⁵
Eligibility											
Informed consent	x										x
Demographic and Medical history	x										x
COVID-19 symptom screen	x										
SARS-CoV-2 RT-PCR for eligibility	x										
Pregnancy test	x										
ABO	x										
Study Drug Administration											
Drug infusion			X								
Study Procedures											
Vital signs ⁴	x	x	Xxxx ³	x	x	x	x	x	x	X	
Physical examination ⁴	x		x	x		x		x		X	
Symptom screen ⁴	x	x	x	x	x	x	x	x	x	X	x
Concomitant medications ⁴	x	x	x	x	x	x	x	x	x	X	
Assessment with 8-point ordinal scale ⁴		x		x	x	x	x	x	x	X	
Adverse event monitoring ⁴		x	x	x	x	x	x	x	X	X	
Health Questionnaire											x
Laboratory testing											
CBC and CMP ⁴		x		x		x	x	x	X	X	X

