7.3.2 Secondary Endpoints

- Cumulative incidence of serious adverse events during the study period: transfusion reaction (fever, rash), transfusion related acute lung injury (TRALI), transfusion associated circulatory overload (TACO), transfusion related infection
- Rates and duration of SARS-CoV-2 PCR positivity at days 0, 4, 7, 14 and 21.
- Serum or plasma antibody titer³ to SARS-CoV-2: Day 0, 7, 14, and 28
- Cellular and humoral immune responses at days 0, 7, 14, and 28 days
- Supplemental oxygen free days
- Ventilator free days
- ICU free days
- Sequential organ failure assessment (SOFA) score at days 0, 1, 4, 7, 14, 21, 28
- WHO 8-point scale for clinical improvement at days 0, 1, 4, 7, 14, 21, 28
- Need for vasopressors
- Need for renal replacement therapy
- Need for extracorporeal membrane oxygenation (ECMO)
- Hospital length of stay (LOS)
- ICU LOS
- Grade 3 or 4 adverse events (AEs)

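### Section 12.8 stops documenting most new AEs 7 days after first infusion, while the visit schedule evaluates AEs through day 60, so late Grade 3 or higher AEs and SAEs not suspected to be related may go uncounted

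*Combined protocol and SAP*

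**What the plan says.** Section 12.8, which sets the interval for recording, states: "All AEs and SAEs will be documented from the first administration of study product and for the following 7 days". Un-enrollment closes the interval earlier if it comes first. Events already documented are followed to resolution, even past this interval. The section ends with a sentence about SAEs that come to light after the 7 days and are suspected to be related, but it breaks off before saying what is to be done with them.

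Other sections run longer:

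- Section 5.2.7 lists "New medical conditions, AE evaluation" for days 1 to 7, again in the follow-up block that extends to day 28, and again at day 60. It also sets study completion at day 60.
- Table 1 (in Section 6.0) has a row for "Adverse event monitoring" that is marked through day 60.
- The Summary gives the assessment days as "Safety and efficacy: Day 0 (baseline), 1, 2, 3, 4, 7, 14, 21, and 28 and once at day 60".
- Section 12.0 itself includes "Clinical evaluations: Vital signs and symptom screen on days 0-7, 14 and symptom screens on days 28, and 60".

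The measures that depend on these data are in 7.3.2 and 9.3. The first is "Cumulative incidence of serious adverse events during the study period", followed by a list: transfusion reaction, TRALI, TACO and transfusion-related infection. The second is Grade 3 or 4 AEs, with no time limit given. Section 9.3 adds: "The proportion of subjects experiencing an SAE and the proportion experiencing a Grade 3 or higher will be recorded". It also gives no time limit, and it plans a comparison of AEs with published data.

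**The concern.** A patient seen on day 14, 21, 28 or 60 is to be evaluated for AEs, but the section that governs recording closes for most new events on day 7. Two study teams could each follow the protocol correctly and report different Grade 3 or higher AE and SAE proportions from the same patients.

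Safety is a stated secondary objective. A comparison with published rates can be interpreted only if the reader knows the period over which events were counted.

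**Working it through.** No power or sample-size figure bears on this point, so the check sets the sections side by side and adds two small counts.

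**1. The recording window.** Under 12.8 it runs from first administration (day 0) to day 0 + 7 = day 7. The follow-to-resolution sentence extends observation of events already recorded. It does not admit new ones.

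**2. The scheduled evaluations.** The AE row of Table 1 has nine marks: baseline, transfusion, and days 1, 4, 7, 14, 21, 28 and 60. Four of these (days 14, 21, 28, 60) fall after day 7. The follow-up outside the window is 60 − 7 = 53 days.

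**3. Whether Table 1 note 4 removes the conflict.** The note attached to the AE row calls for daily assessment through day 7 or discharge. If it were an end date, the four later marks would mean nothing. The same note is attached to the 8-point ordinal scale, which 7.3.2 needs on days 14, 21 and 28. It therefore sets a daily frequency early on and does not close collection.

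**4. Laboratory findings.** Section 10.7 requires clinically significant changes from baseline to be reported as AEs. Table 1 schedules CBC and CMP on days 14, 21, 28 and 60, and Section 12.0 lists safety laboratory tests on day 14. An abnormality first seen on day 14 must be reported under 10.7 but lies outside the 12.8 window.

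**5. What happens to an event that begins after day 7:**

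| Type of event | Documented under 12.8? | Measure affected |
|---|---|---|
| Non-serious AE, Grade 3 or higher | No | Grade 3 or 4 endpoint; 9.3 Grade 3 or higher proportion |
| SAE not suspected to be related | No | 9.3 SAE proportion; also the Grade 3 measures if of that grade |
| SAE suspected to be related | Provision begun, action not stated | 7.3.2 SAE endpoint; 9.3 SAE proportion |
| Death from such an event, not suspected to be related | No | 9.3 SAE proportion only; mortality is counted separately |

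The last row has a visible consequence. Section 12.2 makes death an SAE, so over a common period the SAE proportion cannot be lower than the proportion who died. Under 12.8 it could be.

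**6. Size.** If all 29 planned patients form the denominator, one patient counted or not counted changes a proportion by 1/29 = 3.4 percentage points. The documents give neither AE rates nor times of onset, so no count of missed events can be derived.

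**The case against.** The strongest reply is that the practical reach is narrow, and much of it stands.

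- **Related SAEs.** 12.8 does open a provision for these after day 7, so a flat 7-day limit is not an accurate description for them. The missing end of the sentence may be a fault of the text as read.
- **The SAE endpoint.** The events named in 7.3.2 are all transfusion-related, which is the class that provision addresses. This endpoint is therefore the least exposed of the three measures.
- **The meaning of the study period.** No section defines it, but 5.2.7 puts completion at day 60, and 12.8 uses a different term for its own interval. Day 60 is the natural reading. That helps the endpoint definition but leaves the recording rule in 12.8 unchanged.
- **Deaths.** 28-day mortality is a primary endpoint and 60-day mortality is listed in 8.1. A death from an event documented by day 7 is also covered by follow-up to resolution.
- **Use of the data.** The AE analysis is mainly descriptive. No hypothesis test or sample size depends on it.

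A reader might infer that safety observation ends on day 7, that late deaths go uncounted, or that a large share of the safety data is lost. The documents do not support these readings. The later visits still include AE evaluation, and mortality is captured separately. The four visits after day 7 are 4/7 = 57% of the follow-up columns in Table 1 through day 60, 4/9 = 44% of the post-infusion days in the Summary, or 4/11 = 36% if days 1 to 7 are each counted. The figure depends on the denominator chosen, and it counts visits, not events.

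What the reply does not reach is the first two rows of the table above. Even a completed final sentence in 12.8, on its present subject, would not cover them.

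**Conclusion.** The conflict is established from current text, and no other section resolves it. Followed as written, 12.8 leaves out non-serious Grade 3 or higher AEs, and SAEs not suspected to be related, that start after day 7. The affected measures are the Grade 3 or 4 AE endpoint and the two proportions in 9.3. The error runs in one direction: following 12.8 can only lower these figures relative to following Table 1. Its size is unknown.

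This rests on two assumptions: that 12.8 governs what is entered as an AE, and that the Table 1 marks are read in the right columns. The visit list in 5.2.7 supports the second independently. The point should be corrected, but it does not threaten the primary endpoints.

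Two wording faults nearby are minor. Read literally, 5.2.7 treats any AE before day 60 as completing the study, which is probably a drafting slip because an AE alone is not a listed reason for removal or withdrawal. Section 5.2.7 also starts AE recording at consent, while 12.1 and 12.8 start it at study product; that gap covers only day -1 to 0.

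**What to change.** Reconcile 12.8 with Table 1 by documenting SAEs and Grade 3 or higher AEs through the day 60 visit, and name that window in 7.3.2 and 9.3. If the 7-day limit was meant only for non-serious lower-grade AEs or for the daily checks, say so in 12.8. If the last sentence of 12.8 is also unfinished in the source document, complete it.

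As clean-up, remove the reference to an adverse event from the completion rule in 5.2.7, and use one start point for AE recording in 5.2.7, 12.1 and 12.8.

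These are wording changes. The day 14, 21, 28 and 60 visits already include AE evaluation, so no visit is added. The cost is a modest amount of extra AE data entry.
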